## 5.2 Handling of Study Interventions

**5.2.1 Caloric Restriction Goals:** The calorie level assigned for each person assigned to one of the CR groups will provide him/her with a daily caloric deficit of approximately 20%. The individual absolute calorie level is derived from subtracting 20% from each person's estimated daily energy needs for weight maintenance. The calorie level assigned for each person assigned to one of the CR groups will provide him/her with a daily energy intake (EI) approximately 20% lower than his/her baseline EI. Baseline EI will be determined by measuring Total Energy Expenditure obtained by DLW from Baseline Visit 1 and 2, or through estimating EI using body weight and composition, resting energy expenditure and physical activity level.

*No woman will be prescribed with less than 1100 kcals/d and no man less than 1300 kcals/d.*

## 5.3 Concomitant Interventions

HALLO-P will deliver the step intervention to all 3 groups, using Fitbits to track and feedback activity data to participants via the companion app. The goal will be to promote daily movement; increasing daily steps from baseline. Also, participants will be advised to consume calcium (up to 1200 mg/d) and vitamin D (800 IU/d) supplements to mitigate the risk of BMD loss. The RD will also promote consuming 90 g of protein/day evenly distributed across daily meals in the CR groups; a target monitored via the tracking app for food intake. Finally, a high-quality diet focusing on eating patterns promoting satiety over the fasting period will be recommended to TRE participants.

## 5.4 Adherence Assessment

The primary measure of adherence to the CR regimen will be the change in energy intake from baseline to 9 months calculated using the DLW-measured change in TEE in conjunction with the DXA-measured fat and lean body mass changes over 9 months.

Change in self-reported energy intake will be a secondary adherence measure.

Change in scale-measured body weight in line with our model of expected body mass loss under the assumption of 20% CR is a secondary measure of adherence.

Adherence to the TRE regimen will be assessed through data collected by the Companion App where participants will log occasions of caloric ingestion during waking hours. Participants will be considered compliant if they consumed calories within an 8-hour window on 80% of days. An objective secondary measure of adherence will be through the use of continuous glucose monitoring for 10-day intervals using spiking glucose blood levels as a biomarker of caloric intake.

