### **2.2.1. Rationale for 20% CR**

Reducing caloric intake by 10–40% from *ad libitum* prolongs lifespan in some animal models. Within this range we sought a target that allows for adequate nutrition and is sustainable. In inactive older adults, aggressive CR targets are not feasible because baseline energy intakes are already low. For example, the INFINITE Study included 65–79 year-old sedentary adults with obesity (49). In the group randomized to a 600 kcal/day deficit (~26% CR), 42% of participants would have been prescribed a daily intake of <1100 kcals/d, which is too low to provide adequate overall nutrition. To minimize the loss of skeletal muscle, protein intake of 1.0-1.2 g/kg/day of baseline body weight is recommended (50). In diets with low absolute energy intake, this level of protein consumption can be unpalatable unless protein supplements are provided. The pilot will provide data on baseline energy requirements, the feasibility of formulating palatable and nutritionally adequate meals, and the need to provide protein supplementation. We will use the gold-standard measure of energy expenditure, Doubly-Labeled Water (DLW), in conjunction with Dual X-ray Absorptiometry (DXA)-measured body composition in order to assess energy intake at baseline and 9 months, to document actual CR levels. We will also measure resting energy expenditure (REE) and physical activity energy expenditure (PAEE; via actigraphy) to estimate weight-maintenance energy needs for comparison to DLW values.

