### **3 STUDY DESIGN**

**Overview.** HALLO-P is a 9-month randomized behavioral intervention trial to pilot three strategies to change the amount or timing of food intake in order to evaluate these strategies for use in a long-term trial. The three strategies include 20% CR delivered in-person, 20% CR delivered remotely, and TRE within an 8-hour window each day. All participants will also receive an intervention to reduce sedentary time and increase the number of daily steps.

**Inclusion / Exclusion.** HALLO-P's recruitment target is approximately 100 older (60+ years), community-dwelling men and women residing in Forsyth County, NC or surrounding counties who have obesity ( $BMI = 30 - \leq 40 \text{ kg/m}^2$ ) or are overweight ( $BMI = 27 - <30 \text{ kg/m}^2$ ) with an indication for weight loss (e.g., hypertension, hyperlipidemia, elevated waist girth, controlled diabetes). We will target up to 50% men but expect to be in the range of 35%-45% men, 50%  $> 70$  yrs, and  $> 23\%$  minority participants which reflects racial demographics of our region.

HALLO-P will exclude persons for whom the interventions are potentially unsafe, who have a history of eating or nutritional disorders, who are likely to drop out due to severe chronic illness or other reasons, or who show inability to perform self-monitoring activities required by the interventions. We will exclude those doing shift work because disturbances in circadian cycles may interfere with TRE. We will exclude persons with uncontrolled or previously undetected diabetes because disease management may interfere with the interventions and certain medical treatments may complicate outcome interpretation.

**Randomization / Study Duration.** Recruitment is scheduled to last approximately 12-15 months. Once eligibility is established and baseline testing is completed, participants will be randomized using blocked randomizations stratified by sex to one of the 3 intervention groups for the first 66 participants and blocked randomizations stratified by sex to either the remote CR or TRE groups for the remainder of the cohort. Randomized participants will be in the intervention for 9 months.

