## **9 STATISTICAL CONSIDERATIONS**

### **9.1 General Design Issues**

As suggested by multiple authors (106-108), the design and sample sizes for our HALLO pilot study have been chosen to focus on the feasibility of the design of the targeted full-scale study, rather than on power for hypothesis testing between groups.

During the HALLO pilot, we target the enrollment of approximately 100 participants meeting the inclusion/exclusion criteria to one of three intervention arms 1) 20% CR delivered in-person; 2) 20% CR delivered remotely via video conferencing; and 3) 8-hour TRE with *ad libitum* calorie intake for the first 3 waves (66pts) and the fourth wave will randomize ~24 pp to one of two intervention arms including 20% CR delivered remotely and 8-hour TRE groups. We anticipate randomizing 22:34:34 participants with fewer participants being in the in-person CR group since our group (and others) has more experience with that intervention. From those randomized, we anticipate approximately 20:30:30 participants to complete both pre-and post-measures at 9 months. Data from the enrollment process will be used to refine recruitment criteria, estimate recruitment yields, and test and refine intervention approaches. The pilot will inform three design benchmarks: **a)** The degree of sustained CR (**Benchmark 1**): CR > 10% at 9 months; **b)** TRE sustainability (**Benchmark 2**): At least 75% of participants eating within window on >80% of days; and **c)** **Benchmark 3**: Retention > 85% at 9 months.

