### **9.2 Sample Size and Randomization**

Sample sizes for each group in the pilot study were determined by focusing on the width of 90%, one-sided confidence intervals, as used previously for pilot projects (109). For **Benchmark 1**, the 20% CR interventions will be considered successful if the mean reduction in DLW-assessed weight-maintaining energy intake (EI) provides evidence that the %CR is >10% of the baseline mean (e.g., >200 kcal/day reduction from 2000 kcal/day). This level was chosen because it is approximately the lower end of the range of CR associated with benefits in animal models. Our **primary outcome** will be absolute rather than relative EI change to avoid the loss of efficiency and power from the direct modeling of ratio measures (110, 111). Analyses will be based on constrained, mixed linear models described in Section 9.5. The primary quantity of interest is whether each group's least squares mean EI one-sided 90% lower confidence interval excludes the mean value for an average 10% reduction in caloric intake based on the mean baseline EI.

**Benchmark 1.** Within the remote CR group with ~30 paired observation (i.e., 10% LTFU), and a conservative SD of 250 kcal/day for change in EI, as calculated from CALERIE, we project a 90%, one-sided confidence intervals will have a lower bound excluding 200 kcal/day (a 10% reduction from a baseline mean of 2000 kcal/day) if we observe a 260 kcal/day or greater reduction (a 13% reduction). In a case where the baseline mean intake is 2500 kcal/day, a 310 kcal/day reduction (12.4%) would result in a confidence interval that excludes a 10% reduction in EI (112). With 20 evaluable participants in the in-person CR group, these percentages increase to 13.7% (for a baseline mean of 2000 kcal/day) and 13% (for a baseline mean of 2500 kcal/day). Note that these calculations assume the ICC capturing the dependence of change in EI resulting from group-based interventions is zero. Should the ICC arising from group-based intervention delivery be large enough to inflate the variance of the within-group mean by as much as 10%, a slightly larger observed decrease in EI will be needed to rule out a 10%

reduction. If the target is met for both CR groups, practical and economic considerations will be considered in developing the intervention for the larger trial.

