#### **9.5.4. *Other analyses helpful in planning future longer term studies.***

Additional exploratory analyses will use a variety of analytical techniques to examine: (a) the distribution of changes over time in potential outcomes that may be used as part of a composite outcome in the larger study, (b) how adherence characteristics of TRE are associated with weight change, (c) agreement and potential biases between energy intake targets obtained by initially estimating energy intake necessary for a 20% CR through use of DLW versus based upon using REE and an activity level factor specific to sedentary older adults (or based on observed baseline ActivPAL data) (d) associations between actual weights and expected weights based on the trajectory-based model of the relationship of weight loss to energy intake restriction, and factors associated with discrepancies, and (e) measurement properties (e.g., test-retest reliability, variability in time-course within controls) of selected biomarkers (e.g., of IL6, CRP, TNFR1, Cystatin C, insulin levels).

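### The weight-based adherence measure assumes 20% CR throughout, but the calorie floors assign less than 20% to participants with low baseline intake

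*Combined protocol and SAP*

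**What the plan says.** Section 5.2.1 sets the calorie level in the CR arms at 20% below baseline energy intake (EI), then limits it: "No woman will be prescribed with less than 1100 kcals/d and no man less than 1300 kcals/d".

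Section 5.4 names three adherence measures for CR. The primary one is change in EI from DLW and DXA. Self-reported intake is secondary. The third is change in scale weight in line with "our model of expected body mass loss under the assumption of 20% CR is a secondary measure of adherence". The sentence gives no cut-off and no exception for participants whose prescription is set by a floor.

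Section 9.5.4(d) plans an exploratory comparison of actual with expected weights, using the trajectory-based model "of the relationship of weight loss to energy intake restriction, and factors associated with discrepancies". It names no particular factor.

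Section 2.2.1 explains why low intakes are a concern in inactive older adults. It cites a prior study: "In the group randomized to a 600 kcal/day deficit (~26% CR"), "42% of participants would have been prescribed a daily intake of <1100 kcals/d".

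**The concern.** The floor and the weight reference do not match. Once a floor applies, the assigned deficit is below 20% of baseline EI, but the expected loss is still the one for 20%. A participant who eats exactly what was prescribed should then lose less than the reference predicts and look under-adherent. The error always runs in that direction, and it falls only on participants with low baseline intake.

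Two uses are exposed: the secondary weight-based measure and the comparison in Section 9.5.4(d). In the latter, a gap created by the prescription could be read as behaviour or as misfit of the weight model, and the comparison is meant to inform the longer trial.

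**Working it through.** **Inputs from the documents**
- Floors of 1100 kcal/d (women) and 1300 kcal/d (men): Section 5.2.1.
- Randomized numbers: "We anticipate randomizing 22:34:34 participants" (Section 9.1). The first two arms are CR, so 22 + 34 = 56.
- Sex mix: the investigators "expect to be in the range of 35%-45% men" (Section 3), so 55–65% women.
- Planning mean: "a 10% reduction from a baseline mean of 2000 kcal/day" (Section 9.2), with 2500 kcal/d as the alternative.
- Prior study (Section 2.2.1): a 600 kcal/d deficit described as about 26%, and 42% of participants falling below 1100 kcal/d.

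The plan gives no count of floor-limited participants, so there is no figure of its own to reproduce.

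**Where the floors bind.** The floor applies when 0.8 × EI < floor, that is, EI < floor/0.8.
- Women: 1100/0.8 = 1375 kcal/d.
- Men: 1300/0.8 = 1625 kcal/d.

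**Size for one fully compliant participant.** Assigned deficit = EI − floor; assumed deficit = 0.2 × EI.

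| Participant | Assigned deficit (kcal/d) | Assigned CR | Assumed deficit (kcal/d) | Assumed/assigned |
|---|---|---|---|---|
| Woman, 1350 | 250 | 18.5% | 270 | 1.08 |
| Woman, 1300 | 200 | 15.4% | 260 | 1.30 |
| Woman, 1250 | 150 | 12.0% | 250 | 1.67 |
| Man, 1500 | 200 | 13.3% | 300 | 1.50 |

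These are ratios of deficits. The documents do not give the weight model's output, so the gap in kilograms cannot be stated.

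**How many participants.** This needs assumptions: baseline EI normal within sex, a sex difference *d* of 300–500 kcal/d, and a within-sex SD of 250–300 kcal/d. With overall mean *m* and proportion of women *w*, the women's mean is *m* − (1 − *w*)*d* and the men's is *m* + *wd*. Then

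share = *w*·Φ((1375 − women's mean)/SD) + (1 − *w*)·Φ((1625 − men's mean)/SD).

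At *m* = 2000:
- Low end (*w* = 0.65, *d* = 300, SD = 250): means 1895 and 2195; 0.65·Φ(−2.08) + 0.35·Φ(−2.28) = 1.6%, or 0.9 of 56.
- High end (*w* = 0.55, *d* = 500, SD = 300): means 1775 and 2275; 0.55·Φ(−1.33) + 0.45·Φ(−2.17) = 5.7%, or 3.2 of 56.

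The prior study gives two other anchors. A 600 kcal/d deficit that is 26% of intake implies a mean of 600/0.26 = 2308. A prescription below 1100 after a 600 kcal/d deficit implies baseline EI below 1100 + 600 = 1700, so *m* can instead be solved to put 42% of participants below 1700.

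| Anchor for the mean | Mean EI (kcal/d) | Share floor-limited | Expected number of 56 |
|---|---|---|---|
| Section 9.2, first case | 2000 | 1.6–5.7% | 0.9–3.2 |
| Section 2.2.1, 600 kcal/d as 26% | 2308 | 0.04–0.53% | under 0.3 |
| Section 9.2, second case | 2500 | under 0.1% | under 0.05 |
| Section 2.2.1, 42% below 1700 | 1762–1798 | 11.3–17.6% | 6.3–9.9 |

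Women below 1250 kcal/d, for whom the assumed deficit is more than 1.67 times the assigned one, number 0.2–1.2 of 56 at mean 2000 and 1.9–4.5 under the 42% figure.

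**Averaged over all CR participants.** The ratio 0.2·*m* / E[EI − max(0.8·EI, floor)], with the assigned deficit set to zero where EI is below the floor, exceeds 1 by 0.3–1.4% at mean 2000, by under 0.1% at 2308, and by 3.0–5.9% under the 42% figure.

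**The case against.** The strongest reply is that Section 5.4 offers a one-line description and not an algorithm. Section 5.1.3 calls the weight zones individual to each participant, the table in Section 5.1.2 lists mathematically derived weight goals, and Section 5.1.4 leaves the working rules to an intervention guide that is not part of these documents. The team may already enter the assigned calorie level. That is possible, but none of these places says so, and a zone can be individual in starting weight and baseline EI and still assume 20%. Section 5.2.1 does describe the deficit as approximate, but that does not stretch to 12% or 8%.

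A second reply is that 20% is the dose under study, so weight should be judged against it even where a floor prevented it. The question of dose attained is real, but the DLW/DXA measure already answers it. A woman at 1200 kcal/d is assigned 100/1200 = 8.3% CR. She would match a curve based on her own prescription, while her DLW-based change would still show less than 10%. A measure labelled adherence should compare people with what they were asked to do.

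Several points on the other side stand:
- No decision depends on this measure.
- Section 9.5.4(d) already looks for reasons behind discrepancies, and assigned intake is an obvious candidate.
- Everything needed to recompute the reference is collected, so nothing is lost for good.
- The number affected may be close to zero, and the average effect over the CR arms is small at the planning means.
- The prior study's two figures do not fit together under these assumptions. With a single normal distribution, a mean of 2308 and 42% below 1700 would need an SD of about (2308 − 1700)/0.202, or 3000 kcal/d. The upper end of the range is therefore weakly anchored.
- The BMI entry limit of 27 may thin the lower tail further.

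**Conclusion.** The mismatch is real and follows from the text alone: Section 5.4 fixes the reference at 20% CR, and Section 5.2.1 assigns less than that below 1375 kcal/d for women and 1625 kcal/d for men. It is a minor point. The expected number affected runs from about 0 to 10 of 56, with no single best value; the range rests on the assumed sex difference, SD and normality, and on which anchor for mean intake is used. For an affected complier the assumed deficit exceeds the assigned one by 8% close to the threshold and by 50–67% in the cases further below it. Benchmarks 1 to 3 and the primary adherence measure do not use the weight model and are unchanged.

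**What to change.** In Section 5.4, add one sentence: each participant's expected-weight trajectory is computed from the calorie level actually assigned, max(0.8 × baseline EI, floor). In Section 9.5.4(d), name assigned %CR, or an indicator that a floor applied, among the factors to be examined.

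The cost is that sentence, one changed input to the existing weight model and one named factor. Baseline EI and sex are already collected, so no new data, visit or procedure is needed. Calorie levels, floors, eligibility, Benchmark 1 and the primary adherence measure stay as they are. If the team already uses the assigned level, the edit only records current practice.

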## **6 STUDY PROCEDURES**

## 6.1 Schedule of Evaluations

HALLO Pilot Study Measurements	Phone screen	Screening visit 1	Screening visit 2	Baseline visit 1	Baseline visit 2	Intervention	6-month visit	Intervention	9 month visit 1	9 month visit 2
Visit Code	TSI	SV1	SV2	BV1	BV2	INT	FV1	INT	FV2	FV3
Screening & safety assessments										
Phone screen/phone consent	x									
Screening visit: Informed consent/HIPAA form, demographics, CES-D, Montreal Cognitive Assessment (MoCA), Binge Eating Disorder Screener-7, Readiness to change survey		x							CES-D, MoCA	
7-day behavioral and technology run-in			x							
Vital signs (height/weight/BP/pulse/waist circumference)		x					x		x	
Medical history and medications		x								
Blood lipids, HbA1c, CMP, CBC, TSH		x							x	
Extra tube of blood (SST) for instrument QC		x								
DXA body composition (whole body) / bone density (hip, lumbar spine)		x							x	
Medication Updates/Health Status Updates			x	x	x	x #	x	x #	x	x
Siteman cancer online risk assessment & Cancer Screening Questionnaire							x			
Intervention process and adherence measures & feasibility/acceptability										
Total energy expenditure (TEE; doubly-labeled water)				dose / collect urine	collect urine				dose / collect urine	collect urine
Physical activity energy expenditure (PAEE; ActivPAL)				dis-pense	return				dispense	return
Continuous glucose monitoring (CGM)*						x		x		

HALLO Pilot Study Measurements	Phone screen	Screening visit 1	Screening visit 2	Baseline visit 1	Baseline visit 2	Intervention	6-month visit	Intervention	9 month visit 1	9 month visit 2
Questionnaires/Computerized Task: Power of Food Scale; Weight Efficacy Lifestyle Questionnaire; Food Craving Inventory; SF-36; Perceived Stress Scale; PROMIS 13a Fatigue Scale; Pittsburgh Fatigability Scale; Pittsburgh Sleep Quality Index; PROMIS Interest in Sexual Activity; Emotional & Uncontrolled eating; Walking Self-Efficacy; Delayed Discounting, STOP & Epworth Sleepiness questionnaires				x					x	
Night Eating Assessment				x						
Ecological momentary assessments (EMA) of hunger, desire to eat, and anxiety by study Companion App, Fitbit physical activity monitor, Body Trace smart scale^, App-based dietary tracking^						x		x		
Interview: Positive/Negative Outcomes Associated with CR and TRE, Closeout Survey										x
Clinical/biological outcomes										
Resting energy expenditure (REE)				x					x	
Biomarker assays				x			x		x	
Biological sample storage including blood and urine				x			x		x	
D3 creatine dilution (d3cr)				x					x	
Physical performance/strength: Expanded Short Physical Performance Battery (eSPPB) / expanded SPPB, 400 meter walk (fast), grip strength					x					x
24-hour dietary recalls (ASA24)				x					x	
*- TRE only – at ~3mo (weeks 8-12) and ~8 months (weeks 28-32) ^- CR only # Commons signs and symptoms will also be assessed monthly during intervention at the individual sessions.										

## 6.2 Description of Evaluations

Study evaluations include: 1) assessments of eligibility (Telephone screening interview, Screening Visit 1 and Run-In/Screening Visit 2) and safety (queried at each clinic visit and monthly during intervention), 2) outcome assessments (conducted during two baseline visits, a 6-month follow-up visit, and two 9-month follow-up visits), and 3) assessments of adherence (collected during intervention) according to the schedule in Table 6.1. Details about each evaluation are below. We will follow the above table as best we can but may need to adjust the visit schedule depending on availability of staff, equipment, etc.

**6.2.1. Screening Visit 1 (SV1).** Participants who remain eligible for the study following the phone screening will be scheduled for an in-person Screening Visit to continue assessing the study inclusion/exclusion criteria. Participants will be asked to fast for at least 10 hours the night before this visit and will first sign consent prior to any study measures consisting of the following:

- Vitals (height, weight, BP, pulse, waist circumference)
- Readiness to change survey indicating they are willing to change behavior and comply with intervention
- Blood draw for lipids, comprehensive metabolic panel (CMP), complete blood count (CBC), thyroid stimulating hormone (TSH), HbA1c, and blood for biomarker instrument quality control (20ml or ~1 Tbsp)
- Snack, then whole body, hip, and lumbar spine DXA for body composition and bone density measurements
- Medical history and medications will be ascertained via self-report.
- Questionnaires including the following: demographics, Center for Epidemiological Studies Depression (CES-D), Montreal Cognitive Assessment (MoCA), and the Binge Eating Disorder Screener-7

If blood chemistries, bone densitometry, or any other items measured at the screening visit are exclusionary, the participant will be contacted by the study staff and excused from the study with referral to a health care provider if necessary. Testing may be repeated on a case-by-case basis for re-evaluation.

**6.2.2. Screening Visit 2 (SV2) / Run-in evaluation.** All participants who remain eligible for the study following the SV1 will be scheduled to return for a visit to begin the process of a behavioral run-in. During this visit, participants will be provided with a BodyTrace cellular-enabled scale and an iPad tablet computer. Participants will receive a self-efficacy-based orientation designed to develop confidence in the use of each tool, and will practice weighing using the scale and logging their foods and beverages onto a paper food record. They will be asked to place the scale on a hard and even surface and to weigh daily for 7 days. During this same 7-day period they will also be asked to record the type and amount of food and beverages consumed and document the start and stop time of all foods and beverages each day on a paper log. Participants are asked to take a picture of their paper log and email it to the study team after completing their 7th day to help the assessors determine eligibility prior to their next visit. Participants will receive a “frequently asked questions” handout containing key information for each tool and will receive a follow-up call on the first day of the assessment window (i.e., the

day following SV2) to ensure the participant is able to use the technology and food record. Successfully completing the behavioral run-in will be marked by: 1) completing at least five daily weights, 2) completing five full days of food logging as determined by the study staff and 3) eating at least an average of 11 hours each day.

We will assess for any potential adverse events / change in medical history and medications at this visit as well.

All eligibility will be verified before scheduling or conducting Baseline Visit 1.

We will provide the participant with a tablet with 30mg of d3-creatine and instructions on when to take it 72-144 hours prior to their baseline visit 1. Urine is collected with the participant fasting at their baseline visit 1. Deidentified samples will be sent to [name] laboratory at University California, Berkeley where labeled creatinine will be assayed.

**6.2.3. Baseline Visits 1 and 2.** Following confirmation of meeting all eligibility criteria and after approval to participate from the study clinician or his/her designee, there will be two baseline study visits. The two visits will be conducted after approximately 10-15 days, but ideally between 12-14 days apart to allow for the follow-up collection of urine for the TEE measurement.

Baseline Visit 1 (BV1) evaluation procedures include the participant coming in fasting for the following:

- Blood draw (completed after the REE) and urine collection for biomarker assays and biospecimen archive:
  - Venous blood samples will be collected in the morning following a fast of at least 10 hours. Total blood volume collected is estimated at 69.5 ml (~5 Tbsp) at baseline, including:
    - Serum
    - plasma (EDTA and plasma citrate)
    - whole blood in ACD or CPT tubes for cell and DNA isolation
    - blood in RNA stabilizer tube
  - Urine will be collected per doubly-labeled water assessment of energy expenditure as well as for storage (pre-dose urine will be stored) and for the d3cr.
- Biomarker assays. We will measure pre-specified blood-based biomarkers including but not limited to: fasting insulin, interleukin-6 (IL-6), tumor necrosis factor soluble receptor I (TNFRI), cystatin C, and CRP from serum. Additional biomarkers may be measured using serum, plasma, or urine. This panel will be expanded to include additional biomarkers supported by the NCI supplement and includes the Luminex Performance Human XL Cytokine Panel - NEW (25-Plex) FCSTM18B-25
- DNA methylation biomarker. Cells and blood will be collected for DNA/RNA isolation and molecular measures such as DNA methylation. However, there is no plan to use DNA for genome sequencing; the anticipated use is to measure DNA

CpG site methylation for a biomarker of “epigenetic age” and another candidate aging biomarker, telomere length.

- Biospecimen archive. Serum, plasma, citrate plasma, urine, whole blood, and urine will be collected and stored for use in future ancillary studies. After processing, aliquots will be stored at -80°C or liquid nitrogen until analyses.
- Total Energy Expenditure (TEE) will be assessed using doubly labeled water. This method, which provides the most accurate assessment of free-living daily energy expenditure, is based upon the principle that oxygen atoms in body water and exhaled carbon dioxide are in equilibrium. Oxygen atoms are eliminated from the body as both water ( $H_2O$ ) and exhaled carbon dioxide ( $CO_2$ ), whereas hydrogen atoms are eliminated as water only. The difference between the elimination rates of oxygen and hydrogen from body water represents a measure of carbon dioxide flux, which is proportional to total energy expenditure.

Participants will provide a baseline urine sample after which they will consume a DLW dose which will provide approximately 2.2 g 10%  $H_2^{18}O$  per kilogram total body water and 0.14 g per kilogram total body water of 99%  $^{2}H_2O$ . After consuming the DLW dose, participants will be instructed to lay quietly for approximately 20-30 minutes before initiating the resting energy expenditure test after which further urine samples will be collected approximately 4.5 and 5 hours after dosing, while any urine voids before 4.5 hours will be discarded. Two aliquots of each urine sample will be placed in pre-labeled tubes, stored in freezer boxes at -80°C and shipped in batches to [name] lab at the Advent Health Orlando, Translational Research Institute in Florida for analysis.

- Resting energy expenditure (REE) will be measured in the morning after at least a 10-hour fast using indirect calorimetry (MCG Diagnostics, St. Paul, MN).
- Physical activity energy expenditure (PAEE), including light and moderate to vigorous physical activity as well as sedentary behavior, will be objectively assessed over approximately a 10-15-day period using the ActivPAL™ accelerometer (PAL Technologies, Glasgow, Scotland).
- Dietary intake: 24-hour Dietary Recalls (ASA24) - Three 24-hour dietary recalls (two weekdays and one weekend day) will be collected on all participants. Participants will be asked to recall and report their dietary intake (foods and beverages) from the previous day’s 24-hour period. Participants will complete the first of their 24-hour dietary recalls during the visit and then be prompted to complete 2 additional 24-hour dietary recalls on their own using the study-provided tablet prior to Baseline Visit 2. Data will be collected and nutrients and food groups analyzed using the publicly available National Cancer Institute’s Automated Self-Administered 24-Hour (ASA24) dietary assessment tool (<https://epi.grants.cancer.gov/asa24>).
- We will assess for any potential adverse events / change in medical history and medications at this visit as well.
- Questionnaires

- Power of Food Scale assesses an individual's drive to consume palatable food in an obesogenic food environment (90).
- Weight Efficacy Lifestyle Questionnaire assesses participants' confidence in their ability to self-regulate eating behavior in the face of common barriers (69).
- Perceived Stress Scale assesses how uncontrollable and stressful life has been over the past week or month (91).
- Walking Self-Efficacy assesses participants' perceived ability to walk certain lengths of time at a moderate pace without stopping (92) .
- Quality of Life will be assessed using the *Short Form-36 Health Survey (SF-36)* (93).
- Delayed Discounting assesses participants' ability to delay seeking immediate rewards of less value for longer-term rewards of greater value—delay of gratification (94).
- Food Craving Inventory & Emotional & Uncontrolled Eating(95)
  - An abbreviated emotional and uncontrolled eating questionnaire assesses participants' degree of emotional eating and/or eating in which they feel as though they have lost control.
- Three sleep/fatigue questionnaires will be administered: 1) *PROMIS 13a* (FACIT – Functional Assessment of Chronic Illness Therapy) Fatigue Scale (96); 2) *Pittsburgh Fatigability Scale* (97); and 3) *Pittsburgh Sleep Quality Index* (98)
- Libido will be assessed using the ***PROMIS Interest in Sexual Activity*** questionnaire (99).
- Participants who self-report  $\geq 2$  episodes of Night Eating during the 7-day run-in are identified for potential exclusion due to the night eating syndrome (NES). Participants who do self-report  $\geq 2$  episodes of night eating, are contacted for phone for additional follow-up. Specifically, participants are told that we would like to verify and expand upon information that was provided via the run-in food record data. Using an interview format, participants are queried about night eating using the Night Eating Questionnaire (NEQ) (116).
- Sleep apnea risk will be assessed using the *STOP Questionnaire* (100).
- Sleepiness will be assessed by using the Epworth Sleepiness Scale that assesses how likely someone is to doze off or fall asleep in different situations (101).

**Baseline Visit 2 (BV2).** After approximately 10-15 days, the participant will come to the clinic and will return their ActivPal. Two urine samples will also be collected, at least 30 mins apart, to complete the DLW test for the TEE calculation. At this visit, the participant will be instructed

not to change anything about their diet or exercise behavior prior to the intervention starting. We will also perform the following physical performance/strength tests:

- The Short Physical Performance Battery (SPPB) is a widely used assessment of lower extremity physical function which includes progressively more challenging standing balance tasks held for 10 seconds each (side-by-side, tandem and semi-tandem), the faster of two 4-m walks to assess usual gait speed, and time to complete 5 repeated chair stands. Each of the three performance measures is assigned a score ranging from 0 (inability to do the test) to 4 (the highest level of performance) and summed to create an SPPB summary score ranging from 0 (worst) to 12 (best) (102). We will also administer the components of the *expanded Short Physical Performance Battery (eSPPB)* which was modified from the original SPPB to increase the holding time of the semi- and full-tandem stands to 30 seconds and add a single leg stand and a narrow walk test of balance (walking at usual pace within lines of tape spaced 20 cm apart) (103).
- The fast 400 meter walk is a walking-based test of exercise tolerance and aerobic fitness. Participants are instructed to walk 400 m (10 laps of a 20-m course) on a flat indoor surface as quickly as possible at a maintainable pace and the time to complete the walk is recorded in minutes and seconds (103).
- Grip strength will be measured twice in each hand using an isometric hydraulic hand dynamometer (Jamar, Bolingbrook, IL). Participants will be excluded from performing the test if they report hand-pain or recent hand or wrist surgery.

We will assess for any potential adverse events / change in medical history and medications at this visit as well.

